1.1 How will you define adverse events (AE) for this study?

X An adverse event will be considered any undesirable sign, symptom or medical or psychological condition **even if the event is not considered to be related** to the investigational drug/device/intervention. Medical condition/diseases present before starting the investigational drug/intervention will be considered adverse events only if they worsen after starting study treatment/intervention. An adverse event is also any undesirable and unintended effect of research occurring in human subjects as a result of the collection of identifiable private information under the research. Adverse events also include any problems associated with the use of an investigational device that adversely affects the rights, safety or welfare of subjects.

1.2 How will you define serious adverse events?

X A serious adverse event will be considered any undesirable sign, symptom, or medical condition which is fatal, is life-threatening, requires or prolongs inpatient hospitalization, results in persistent or significant disability/incapacity, constitutes a congenital anomaly or birth defect, is medically significant and which the investigator regards as serious based on appropriate medical judgment. An important medical event is any AE that may not result in death, be life-threatening, or require hospitalization but may be considered an SAE when, based upon appropriate medical judgment, it may jeopardize the patient and may require medical or surgical intervention to prevent one of the outcomes listed in the definitions of SAEs.

1.3 What is the definition of an unanticipated problem?

An unanticipated problem is any event, experience that meets ALL 3 criteria below:

- Is unexpected in terms of nature, severity or frequency given the research procedures that are described in the protocol-related documents AND in the characteristics of the subject population being studied
- Related or possibly related to participation in research. This means that there is a reasonable possibility that the incident may have been caused by the procedures involved in the research study.

IRB-HSR# 13789: **Effect of Metformin on Sensitivity of the GnRH Pulse Generator to Suppression by Estradiol and Progesterone in Hyperandrogenic Adolescent Girls**

- The incident suggests that the research placed the subject or others at greater risk of harm than was previously known or recognized OR results in actual harm to the subject or others

1.4 What is the definition of a protocol violation?

A protocol violation is defined as any change, deviation, or departure from the study design or procedures of a research project that is NOT approved by the IRB-HSR prior to its initiation or implementation, OR deviation from standard operating procedures, Good Clinical Practices (GCPs), federal, state or local regulations. Protocol violations may or may not be under the control of the study team or UVa staff. These protocol violations may be major or minor violations.

Additional Information: see the IRB-HSR website at http://www.virginia.edu/vpr/irb/HSR_docs/Forms/Protocol_Violations_%20Enrollment_Exceptions_Instructions.doc

1.5 If pregnancy occurs how will this information be managed?

X Adverse Event- will follow adverse event recording and reporting procedures outlined in section 3.

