If admission is scheduled to occur greater than one month after the most recent hemoglobin (such as that obtained during screening), a hemoglobin will be repeated 2-5 days before the overnight admission. Documentation of hemoglobin ≥ 11.5 g/dL for non-African American subjects and documentation of hemoglobin ≥ 11.0 g/dL for African American subjects in the previous month is required for the frequent sampling protocol. If overnight admission is scheduled to occur greater than 3 months after screening, then the safety labs (complete blood count, comprehensive metabolic panel) will be repeated at this time.

Day 0: Admission #1

Note:

- Admission #1 will occur on Day 7-11 of the cycle in girls who are cycling with some regularity and on day ≥ 7 in those with infrequent cycles (girls with < 10 cycles per year) provided they have a progesterone level of < 1.5 ng/mL within 3 days of their scheduled first admission. If the progesterone level is >1.5 ng/mL within 3 days of the first admission, the first admission will be cancelled.

IRB-HSR# 13789: Effect of Metformin on Sensitivity of the GnRH Pulse Generator to Suppression by Estradiol and Progesterone in Hyperandrogenic Adolescent Girls

- At each overnight admission a urine HCG will be done to rule out pregnancy and must be negative for the study to continue.

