Starting the day of discharge from Admission #2, subjects will begin taking Metformin 500 mg daily.

Day 14: Increase Metformin dose

On Day 14, the dose of Metformin will be increased to 500 mg twice a day. The subjects will be contacted by phone to inquire regarding adverse events related to the metformin and to remind them to increase the dose of the medication.

Day 21: Increase Metformin dose

On Day 21, the dose of Metformin will be increased to 1000 mg in the morning and 500 mg at night. The subjects will be contacted by phone to inquire regarding adverse events related to the metformin and to remind them to increase the dose of the medication.

Day 28: Increase Metformin dose

On Day 28, the dose of Metformin will be increased to 1000 mg twice a day. The subjects will be contacted by phone to inquire regarding adverse events related to the metformin and to remind them to increase the dose of the medication.

Day 42-49: Outpatient blood draw

Girls will come in after an overnight (>8 hour) fast and have blood drawn for testosterone, SHBG, fasting insulin, fasting glucose, and comprehensive metabolic panel.

Day 84: Admission #3

Note: Admission #3 is timed to the subject's cycles, and therefore is unlikely to occur exactly on Day 84. All girls will take at least 11 weeks (77 days) of Metformin and will then come in for admission #3 at the first appropriate time in their cycle, which will be either on Day 7-11 of their cycle or day ≥ 7 in those with infrequent cycles (girls with < 10 periods per year) provided they have a progesterone level of < 1.5 ng/mL within 3 days of their scheduled first admission. If the progesterone level is >1.5 ng/mL within 3 days of the first admission, the admission will be cancelled.

Admission #3 will be identical to Admission #1. Subjects will be instructed to eat a diet including at least 150 gm of carbohydrate a day for the 3 days preceding the admission

IRB-HSR# 13789: **Effect of Metformin on Sensitivity of the GnRH Pulse Generator to Suppression by Estradiol and Progesterone in Hyperandrogenic Adolescent Girls**

Day 85: Begin Estradiol and Progesterone

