NOTE: Risk of unplanned pregnancy: If a research subject is sexually active and stops using hormonal contraception while failing to use another non-hormonal method of contraception, there is a risk of unplanned pregnancy. (However, subjects will be counseled to use non-hormonal methods of contraception if sexually active.)

NOTE regarding the risk associated with EMLA cream (topical lidocaine and prilocaine, used to alleviate pain): The risks of lidocaine and prilocaine in general may include (frequency not defined) hypotension, angioedema, shock, hyperpigmentation, erythema, itching, rash, burning, urticaria, burning, stinging, edema, bronchospasm, and hypersensitivity reactions. However, in the case of topical lidocaine/prilocaine use, the non-dermatologic adverse events mentioned above would be extremely unlikely unless large amounts of topical lidocaine/prilocaine were used (allowing significant systemic absorption).

2.2 List by bullet format a summary of safety tests/procedures/observations to be performed.

- Sterile technique will be used.
- Before participation in the studies, all participants will be required to have a normal hemoglobin (≥ 11.5 g/dL for non-African American subjects and ≥ 11.0 g/dL for African American subjects). Hemoglobin levels will be measured prior to every admission. For African American subjects, if the hemoglobin level is < 11.0 , the study will be discontinued. For non-African American subjects, if the hemoglobin level is < 11.5 g/dl, the study will be discontinued.
- Blood loss will be carefully recorded and limited to a maximum of 7cc/kg (10% of estimated total blood volume) in 8 weeks. A total of 467 ml of blood will be drawn during the study (including estimated waste from frequent blood draws), with no more than 243.5 being drawn during any 8 week period. Therefore, girls weighing less than 35 kg will not be able to participate. Iron supplementation (325 mg once or twice a day dependent on weight) will be prescribed to all participants.
- We will warn participants against becoming pregnant during the study. We will require that sexually active subjects use effective double barrier methods of birth control as needed during the study. β -hCG levels will be measured at screening and prior to each admission; if the β -hCG is positive, the study will be discontinued.

2.3 Under what criteria would an INDIVIDUAL SUBJECT'S study treatment or study participation be stopped or modified

At subject, PI or sponsor's request

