3.6 When will the recording/reporting of adverse events/unanticipated problems end?

End of study drug/device/intervention/participation

IRB-HSR# 13789: Effect of Metformin on Sensitivity of the GnRH Pulse Generator to Suppression by Estradiol and Progesterone in Hyperandrogenic Adolescent Girls

 X 30 days post study drug

3.7 How will Adverse Events, Unanticipated Problems, Protocol Violations and Data Breaches be reported? Complete the table below to answer this question

Type of Event	To whom will it be reported:	Time Frame for Reporting	How reported?
Any internal event resulting in death that is deemed DEFINITELY related to (caused by) study participation An internal event is one that occurs in a subject enrolled in a UVa protocol	IRB-HSR	Within 24 hours	IRB Online and phone call www.irb.virginia.edu/
Internal, Serious, Unexpected adverse event	IRB-HSR	Within 7 calendar days from the time the study team received knowledge of the event. Timeline includes submission of signed hardcopy of AE form.	IRB Online www.irb.virginia.edu/
Unanticipated Problems that are not adverse events or protocol violations This would include a Data Breach.	IRB-HSR	Within 7 calendar days from the time the study team received knowledge of the event.	Unanticipated Problem report form. http://www.virginia.edu/vprgs/irb/HSR_docs/Forms/Reporting_Requirements-Unanticipated_Problems.doc)
Protocol Violations (The IRB-HSR only requires that MAJOR violation be reported, unless otherwise required by your sponsor, if applicable.) Or Enrollment Exceptions	IRB-HSR	Within 7 calendar days from the time the study team received knowledge of the event.	Protocol Violation and Enrollment Exception Reporting Form http://www.virginia.edu/vprgs/irb/hsr_forms.html Go to 3rd bullet from the bottom.

IRB-HSR# 13789: Effect of Metformin on Sensitivity of the GnRH Pulse Generator to Suppression by Estradiol and Progesterone in Hyperandrogenic Adolescent Girls

Data Breach	The UVa Corporate Compliance and Privacy Office, a	As soon as possible and no later than 24 hours from the time the incident is identified.	UVa Corporate Compliance and Privacy Office- [contact]
	ITC: if breach involves electronic data-	As soon as possible and no later than 24 hours from the time the incident is identified.	ITC: Information Security Incident Reporting procedure, http://www.itc.virginia.edu/security/reporting.html

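### Adverse-event recording ends 30 days after study drug, before any birth from an exposed pregnancy on the nominal schedule, and no pregnancy test is scheduled in the 77 or more days of metformin between Admissions 2 and 3

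*Combined protocol and SAP*

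**What the plan says.** All section numbers below refer to the Data and Safety Monitoring Plan in the combined protocol and SAP.

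- **Handling of pregnancy (1.5):** "Adverse Event- will follow adverse event recording and reporting procedures outlined in section 3".
- **End of recording (3.6):** the option that carries a visible mark is "30 days post study drug". A second option, "End of study drug/device/intervention/participation", is printed without a visible mark.
- **Seriousness (1.2):** an event is serious if, among other criteria, it "constitutes a congenital anomaly or birth defect".
- **Testing:** section 2.2 says of β-hCG that "levels will be measured at screening and prior to each admission". The notes to Admission #1 add: "At each overnight admission a urine HCG will be done to rule out pregnancy and must be negative for the study to continue".
- **Metformin:** "Starting the day of discharge from Admission #2, subjects will begin taking Metformin 500 mg daily". At least 77 days of metformin precede Admission #3, which then waits for the right cycle timing and a low progesterone level.
- **Visit in between (Day 42-49):** the girls "have blood drawn for testosterone, SHBG, fasting insulin, fasting glucose, and comprehensive metabolic panel". hCG is not on the list.
- **Safeguards:** pregnant girls are excluded, sexually active girls must abstain or use double barrier contraception, and a positive test ends participation (Inclusion/Exclusion Criteria; 2.2; 2.3).
- **After the study (Follow-up):** an optional year, with questionnaires or calls at 6 and 12 months on menses and hirsutism and, where possible, one or two blood draws. The blood list has no hCG, and no item asks about a pregnancy or its outcome.

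**The concern.** The plan names a birth outcome as serious, sends pregnancies down the adverse-event route, and ends that route 30 days after the last dose. Nothing in the plan follows a pregnancy to its outcome. A site that does exactly what is written would close the file on an exposed pregnancy months before the outcome could be known.

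The second issue is detection. Participation requires girls on oral contraceptives to stop them for three months, and section 2.1 itself lists unplanned pregnancy as a risk for girls who stop hormonal contraception without using another method. The study also expects some girls with fewer than 10 cycles a year, in whom a missed period is a weak signal. A conception soon after Admission #2 could go untested until Admission #3.

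At stake is the completeness of the safety record, not the efficacy result.

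**Working it through.** **Inputs from the documents.** Admissions on nominal Days 0, 7, 84 and 91; metformin from Day 8; at least 77 days of metformin before Admission #3; all study drugs stopped after the final draw of Admission #4, which falls on the morning after a Day 91 admission (Day 92); recording ends 30 days after study drug.

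**Assumption not in the documents.** Conception to birth takes 259 to 280 days at term; 140 days serves as an extreme preterm case.

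**1. The plan's own interval.** 11 weeks × 7 = 77 days, and Day 84 − Day 7 = 77 days. The stated figure is reproduced.

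**2. Gaps between scheduled tests after Day 0.** 7 − 0 = 7; 84 − 7 = 77; 91 − 84 = 7 days. The 77 days is a minimum on the test-at-admission reading, because Admission #3 has no stated latest date. If the test is done shortly before the admission, as section 2.2 can be read, the gap shortens by that much. The Day 42-49 draw lies 42 − 7 = 35 to 49 − 7 = 42 days after Admission #2, and 84 − 49 = 35 to 84 − 42 = 42 days before nominal Admission #3.

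**3. Closure of recording against date of birth.** Closure = last drug day + 30. Birth = conception day + 259 to 280. The earliest term birth, for conception on Day 8, is 8 + 259 = Day 267.

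| Last drug day | Closure | Latest term birth | Birth after closure |
|---|---|---|---|
| 84 (positive test at Admission #3) | 114 | 84 + 280 = 364 | 267 − 114 = 153 to 364 − 114 = 250 days |
| 91 (Admission #4) | 121 | 91 + 280 = 371 | 267 − 121 = 146 to 371 − 121 = 250 days |
| 92 (morning after Admission #4) | 122 | 371 | 267 − 122 = 145 to 371 − 122 = 249 days |

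For conceptions on drug, the shortfall is 145 to 250 days. If a girl stops on Day 84 for another reason and conceives on Day 91, it reaches 371 − 114 = 257 days.

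**4. Sensitivity.**

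- *Very early birth.* Conception on Day 8 with birth at 140 days gives Day 148, which is 26 to 34 days after closure (148 − 122; 148 − 114). Even conception 14 days before Admission #1 with birth at 140 days gives Day 126, still 4 to 12 days after closure.
- *Late Admission #3.* A term birth on Day 267 would fall inside a window closing 30 days after Admission #3 only if that admission took place on Day 267 − 30 = 237 or later. That is 237 − 84 = 153 days behind schedule.

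On the nominal schedule, no birth falls inside the 30-day window.

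**5. The unmarked option in 3.6.** Suppose it also applies and participation covers the optional year, ending near Day 91 + 365 = 456. Births on Days 267 to 371 would then fall inside for girls who opt in. The follow-up still asks about menses and hirsutism only, and the plan does not say whether a girl stopped for pregnancy enters it.

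**The case against.** The best defence is that pregnancy is well guarded against. Pregnant girls are excluded, sexually active girls must abstain or use double barrier methods and are counselled on non-hormonal contraception, and hCG is tested before each drug course begins: Admission #1 before estradiol and progesterone, Admission #2 before metformin, Admission #3 before the second hormone course. A positive test ends participation. With 60 girls aged 10 to 17 enrolled, few cases are likely. All of this stands. It lowers the number of cases, but it does not supply an outcome for those that occur.

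Some stronger readings are tempting but are not supported:

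- *Pregnancy is handled only as an adverse event.* That describes how the information is recorded; the safeguards above are also part of the plan.
- *A birth defect can never be captured.* An anomaly seen antenatally, or at a loss within 30 days of the last dose, could be recorded, and the second option in section 3.6 may have lost its mark in text extraction.
- *A pregnant girl could take a rising dose for 11 weeks untested.* Dose increases end on Day 28, and the dose is constant afterwards.
- *The plan contradicts itself.* Section 1.2 classifies events that come to notice; it does not promise to follow every pregnancy to term. The defect is a definition without a matching recording rule.
- *Nothing happens after the study except two calls.* The optional year also allows one or two blood draws, and a question about menses might bring a pregnancy to light.

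Consent pages were removed from the text, so pregnancy wording there cannot be excluded. The documents give no pregnancy rate and no fetal-risk figure, so the expected number of affected cases cannot be calculated.

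**Conclusion.** The point holds in two limited parts.

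First, under the marked 30-day rule, a birth defect found at birth would normally fall outside recording by about 145 to 257 days. The size depends on the assumed gestation and the nominal calendar; the direction holds across the gestations tried. If the unmarked option in section 3.6 also applies, the window may be long enough for girls who join the optional follow-up, but no planned question or test would elicit the outcome.

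Second, no pregnancy test is scheduled in the 77 or more days of metformin between Admissions #2 and #3.

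Few cases are expected and the primary contrast is untouched. This is a worthwhile, low-cost improvement to the safety record, not a flaw that threatens the trial's conclusions.

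**What to change.** 1. **Reconcile sections 1.2, 1.5 and 3.6.** State that a pregnancy detected from first study drug until 30 days after the last has its outcome recorded beyond the 30-day limit, with permission, and through the planned follow-up contacts where possible. Make clear in section 3.6 which end-of-recording options apply.
2. **Add an hCG assay to the existing Day 42-49 sample** as safety monitoring. This would divide the nominal 77-day gap into two intervals of about 35 to 42 days each. The rule in section 2.3 for a positive test stays as it is; no dose or treatment rule changes.

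The cost is a short amendment, one inexpensive assay per girl at a visit where blood is already drawn, and consent and assent wording for outcome follow-up, to be used only in the few affected cases.

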1.6 What is the definition of a Protocol Enrollment Exception?

X NA- No outside sponsor

1.7 What is the definition of a data breach?

A data breach is defined in the HITECH Act (43 USC 17932) as an unauthorized acquisition, access, or use of protected health information (PHI) that compromises the security or privacy of such information.

Additional Information may be found on the IRB-HSR Website: [Data Breach](#)

2. Identified risks and plans to minimize risk

2.1 What risks are expected due to the intervention in this protocol?

Risk associated with frequent blood sampling:

Expected Risks related to study participation.	Frequency Please pick one frequency from each box below

 significant anemia related to frequent blood sampling (hematocrit < 30%) 	 Occurs frequently,  Occurs infrequently  Occurs rarely  Frequency unknown, but very rare

 mild anemia (hematocrit < 36%) related to frequent blood sampling 	 Occurs frequently,  Occurs infrequently  Occurs rarely  Frequency unknown

Risk associated with IV needle placement:

Expected Risks related to study participation.	Frequency Please pick one frequency from each box below

IRB-HSR# 13789: Effect of Metformin on Sensitivity of the GnRH Pulse Generator to Suppression by Estradiol and Progesterone in Hyperandrogenic Adolescent Girls

 Infection at needle site 	 Occurs frequently,  Occurs infrequently  Occurs rarely  Frequency unknown, but very rare

 Fainting 	 Occurs frequently,  Occurs infrequently  Occurs rarely  Frequency unknown, but very rare

 Bleeding at needle site 	 Occurs frequently,  Occurs infrequently  Occurs rarely  Frequency unknown

 Blood clot at needle site 	 Occurs frequently,  Occurs infrequently  Occurs rarely  Frequency unknown

 Pain at needle site 	 Occurs frequently,  Occurs infrequently  Occurs rarely  Frequency unknown

 Bruise at needle site 	 Occurs frequently,  Occurs infrequently  Occurs rarely  Frequency unknown

Risks associated with iron supplementation:

Expected Risks related to study participation.	Frequency Please pick one frequency from each box below

 nausea 	 Occurs frequently,  Occurs infrequently  Occurs rarely  Frequency unknown

 constipation 	 Occurs frequently,  Occurs infrequently  Occurs rarely  Frequency unknown

 dark or black stools 	 Occurs frequently,  Occurs infrequently  Occurs rarely  Frequency unknown

Risks associated with Progesterone:

Expected Risks related to study participation.	Frequency Please pick one frequency from each box below

 Mood changes/irritability 	 Occurs frequently,  Occurs infrequently  Occurs rarely  Frequency unknown

 Fluid retention 	 Occurs frequently,  Occurs infrequently  Occurs rarely  Frequency unknown

IRB-HSR# 13789: Effect of Metformin on Sensitivity of the GnRH Pulse Generator to Suppression by Estradiol and Progesterone in Hyperandrogenic Adolescent Girls

 Withdrawal bleeding 1-5 days after stopping progesterone 	 Occurs frequently,  Occurs infrequently  Occurs rarely  Frequency unknown
--	--

Risks associated with Estradiol:

Expected Risks related to study participation.	Frequency Please pick one frequency from each box below

 Nausea 	 Occurs frequently,  Occurs infrequently  Occurs rarely  Frequency unknown

 Fluid retention 	 Occurs frequently,  Occurs infrequently  Occurs rarely  Frequency unknown

 Breast Tenderness 	 Occurs frequently,  Occurs infrequently  Occurs rarely  Frequency unknown

 Deep vein thrombosis 	 Occurs frequently,  Occurs infrequently  Occurs rarely  Frequency unknown, however occurs very rarely with long-term estrogen use (as with oral contraceptive pills), so would expect to be exceedingly rare with the short term administration in this protocol

Risks associated with Metformin:

Expected Risks related to study participation.	Frequency

 Diarrhea 	 Occurs frequently,  Occurs infrequently  Occurs rarely  Frequency unknown

 Nausea 	 Occurs frequently,  Occurs infrequently  Occurs rarely  Frequency unknown

 Lactic Acidosis 	 Occurs frequently,  Occurs infrequently  Occurs rarely  Frequency unknown, but very rare

Other Risks:

Expected Risks related to study participation.	Frequency
Reproductive Risks	Minimized due to the requirements of this

IRB-HSR# 13789: Effect of Metformin on Sensitivity of the GnRH Pulse Generator to Suppression by Estradiol and Progesterone in Hyperandrogenic Adolescent Girls

Specify potential reproductive risks	protocol.
Violation of subject's privacy and confidentiality	Minimized due to the requirements of the privacy plan in this protocol

NOTE: Risk of unplanned pregnancy: If a research subject is sexually active and stops using hormonal contraception while failing to use another non-hormonal method of contraception, there is a risk of unplanned pregnancy. (However, subjects will be counseled to use non-hormonal methods of contraception if sexually active.)

NOTE regarding the risk associated with EMLA cream (topical lidocaine and prilocaine, used to alleviate pain): The risks of lidocaine and prilocaine in general may include (frequency not defined) hypotension, angioedema, shock, hyperpigmentation, erythema, itching, rash, burning, urticaria, burning, stinging, edema, bronchospasm, and hypersensitivity reactions. However, in the case of topical lidocaine/prilocaine use, the non-dermatologic adverse events mentioned above would be extremely unlikely unless large amounts of topical lidocaine/prilocaine were used (allowing significant systemic absorption).

2.2 List by bullet format a summary of safety tests/procedures/observations to be performed.

- Sterile technique will be used.
- Before participation in the studies, all participants will be required to have a normal hemoglobin (≥ 11.5 g/dL for non-African American subjects and ≥ 11.0 g/dL for African American subjects). Hemoglobin levels will be measured prior to every admission. For African American subjects, if the hemoglobin level is < 11.0 , the study will be discontinued. For non-African American subjects, if the hemoglobin level is < 11.5 g/dl, the study will be discontinued.
- Blood loss will be carefully recorded and limited to a maximum of 7cc/kg (10% of estimated total blood volume) in 8 weeks. A total of 467 ml of blood will be drawn during the study (including estimated waste from frequent blood draws), with no more than 243.5 being drawn during any 8 week period. Therefore, girls weighing less than 35 kg will not be able to participate. Iron supplementation (325 mg once or twice a day dependent on weight) will be prescribed to all participants.
- We will warn participants against becoming pregnant during the study. We will require that sexually active subjects use effective double barrier methods of birth control as needed during the study. β -hCG levels will be measured at screening and prior to each admission; if the β -hCG is positive, the study will be discontinued.

2.3 Under what criteria would an INDIVIDUAL SUBJECT'S study treatment or study participation be stopped or modified

At subject, PI or sponsor's request

Treatment would be stopped if the subject had a serious adverse event deemed related to study.

Other: The study would be stopped if the patient has a positive pregnancy test or if hemoglobin levels were below the required levels (For African American subjects, they must have a hemoglobin of ≥ 11.0 . For non-African American subjects, they must have a hemoglobin of ≥ 11.5).

2.4 Under what criteria would THE ENTIRE STUDY need to be stopped.

These are called stopping rules for early termination of the entire study.

IRB-HSR# 13789: Effect of Metformin on Sensitivity of the GnRH Pulse Generator to Suppression by Estradiol and Progesterone in Hyperandrogenic Adolescent Girls

*List criteria regardless of whether the study is sponsored or not.
Be sure to include any criteria for which the UVa PI would halt the study at UVa.*

Per IRB, PI, DSMB, or sponsor discretion

Other: If there are an excessive number of unexpected adverse events that significantly alter the risk/benefit ratio for the study, the study will be terminated. All adverse events will be evaluated both individually and cumulatively by the study team and principal investigator as they arise, allowing for timely decisions regarding study continuation/termination.

